# 10.3.5 Assessment of Intensity

The Investigator will make an assessment of intensity for each AE reported during the study. An intensity grade will be assigned to each AE. The intensity grading scales used in this study are adapted from the "FDA Guidance for Industry: Toxicity Grading Scale for Healthy Adult and Adolescent Volunteers Enrolled in Preventive Vaccine Clinical Trials, September 2007".

#### **10.3.5.1** Tables for Clinical Abnormalities

# 10.3.5.1.1 Solicited AR Intensity Grading Scale

Table 10.1 Solicited injection site reactions: terminology, definitions, and intensity scales

CRB term (MedDRA lowest level term [LLT])	Injection site pain	Injection site erythema	Injection site swelling
Diary card term	Pain	Redness	Swelling
Definition	Pain either present spontaneously or when the injection site is touched or injected limb is mobilized	Presence of a redness including the approximate point of needle entry	Swelling at or near the injection site  Swelling or edema is caused by a fluid infiltration in tissue or cavity and, depending on the space available for the fluid to disperse, swelling may be either soft (typically) or firm (less typical) to touch and thus can be best described by looking at the size of the swelling

Intensity scale*	CRB:	Grade 1: ≥ 25 to ≤ 50 mm	Grade 1: ≥ 25 to ≤ 50 mm
	Grade 1: A type of adverse event that is	Grade $2: \ge 51$ to $\le 100$ mm	Grade $2: \ge 51$ to $\le 100$ mm
	usually transient and may require only minimal treatment or therapeutic intervention. The event does not generally interfere with usual activities of daily living.	Grade 3: > 100 mm	Grade 3: > 100 mm
	Grade 2: A type of adverse event that is usually alleviated with additional therapeutic intervention. The event interferes with usual activities of daily living, causing discomfort but poses no significant or permanent risk of harm to the research participant.		
	Grade 3: A type of adverse event that interrupts usual activities of daily living, or significantly affects clinical status, or may require intensive therapeutic intervention.		
	Diary card:		
	Grade 1: No interference with usual activities		
	Grade 2: Some interference with usual activities		
	Grade 3: Significant; prevents usual activities		

MedDRA: Medical Dictionary for Regulatory Activities

\* For the scale will be provided in the CRF and the intensity will be transcribed from in the diary card. For other injection site reactions (erythema and swelling), the classification as Grades 1, 2, or 3 will be applied at the time of statistical analysis; the scale is provided for information purposes only. The actual size of the reaction will be reported in the CRF.

Table 10.2: Solicited systemic reactions: terminology, definitions, and intensity scales

CRB term (MedDRA lowest level term [LLT])	Fever	Headache	Malaise	Myalgia	
Diary card term	Temperature	Headache	Feeling unwell	Muscle aches and pains	
Definition Elevation of temperature to ≥°38.0°C (≥ 100.4°F)		Pain or discomfort in the head or scalp. Does not include migraine.	General ill feeling.  Malaise is a generalized feeling of discomfort, illness, or lack of wellbeing that can be associated with a disease state. It can be accompanied by a sensation of exhaustion or inadequate energy to accomplish usual activities.	Muscle aches and pains are common and can involve more than one muscle at the same time.  Muscle pain can also involve the soft tissues that surround muscles.  These structures, which are often referred to as connective tissues, include ligaments, tendons, and fascia (thick bands of tendons).  Does not apply to muscle pain at	
				the injection site which should be reported as injection site pain.	
Intensity scale*	Grade 1: $\geq 38.0$ °C to $\leq 38.4$ °C,	CRB:	CRB:	CRB:	
	or ≥ 100.4°F to ≤ 101.1°F	Grade 1: A type of adverse event that is usually transient and may require only minimal treatment or therapeutic intervention. The event does not generally interfere with usual activities of daily living.	Grade 1: A type of adverse event that is usually transient and may require only minimal treatment or therapeutic intervention. The event does not generally interfere with usual activities of daily living.	Grade 1: A type of adverse event that is usually transient and may require only minimal treatment or therapeutic intervention. The event does not generally interfere with usual activities of daily living.	

Grade $2: \ge 38.5^{\circ}\text{C}$ to $\le 38.9^{\circ}\text{C}$ , or $\ge 101.2^{\circ}\text{F}$ to $\le 102.0^{\circ}\text{F}$	Grade 2: A type of adverse event that is usually alleviated with additional therapeutic intervention. The event interferes with usual activities of daily living, causing discomfort but poses no significant or permanent risk of harm to the research participant.	Grade 2: A type of adverse event that is usually alleviated with additional therapeutic intervention. The event interferes with usual activities of daily living, causing discomfort but poses no significant or permanent risk of harm to the research participant.	Grade 2: A type of adverse event that is usually alleviated with additional therapeutic intervention. The event interferes with usual activities of daily living, causing discomfort but poses no significant or permanent risk of harm to the research participant.
Grade 3: ≥ 39.0°C or ≥ 102.1°F	Grade 3: A type of adverse event that interrupts usual activities of daily living, or significantly affects clinical status, or may require intensive therapeutic intervention.	Grade 3: A type of adverse event that interrupts usual activities of daily living, or significantly affects clinical status, or may require intensive therapeutic intervention.	Grade 3: A type of adverse event that interrupts usual activities of daily living, or significantly affects clinical status, or may require intensive therapeutic intervention.
	Diary card: Grade 1: No interference with usual activities Grade 2: Some interference with usual activities Grade 3: Significant; prevents usual activities	Diary card: Grade 1: No interference with usual activities Grade 2: Some interference with usual activities Grade 3: Significant; prevents usual activities	Diary card: Grade 1: No interference with usual activities Grade 2: Some interference with usual activities Grade 3: Significant; prevents usual activities

MedDRA: Medical Dictionary for Regulatory Activities

\* For all reactions (except fever), the scale will be provided in the CRF and the intensity will be transcribed from the diary card. For fever, will be recorded will be recorded, and the classification as Grade 1, 2, or 3 will be assigned at the time of the statistical analysis based on the unit used to measure the temperature and the intensity scale.

#### Important notes for the accurate assessment of temperature:

Participants are to measure body temperature once per day, preferably always at the same time. The optimal time for measurement is the evening, when body temperature is the highest. Temperature is also to be measured at the time of any apparent fever. The observed daily temperature and the route of measurement are to be recorded in the eDC and the highest temperature will be recorded by the site in the CRF. The preferred route for this study is oral.

#### 10.3.5.1.2 Unsolicited AE Intensity Grading Scale

For measurable unsolicited AEs that are part of the list of solicited reactions, the corresponding scale for solicited reactions will be used (see Section 10.3.5.1.1).

All other unsolicited AEs will be classified according to the following intensity scale:

- Grade 1
  - CRF: A type of adverse event that is usually transient and may require only minimal treatment or therapeutic intervention. The event does not generally interfere with usual activities of daily living.
  - Diary card: No interference with usual activities.
- Grade 2
  - CRF: A type of adverse event that is usually alleviated with additional therapeutic intervention. The event interferes with usual activities of daily living, causing discomfort but poses no significant or permanent risk of harm to the research participant.
  - Diary card: Some interference with usual activities.
- Grade 3
  - CRF: A type of adverse event that interrupts usual activities of daily living, or significantly affects clinical status, or may require intensive therapeutic intervention.
  - Diary card: Significant; prevents usual activities.

# 10.3.5.2 Tables for Laboratory Abnormalities

The pre-defined intensity thresholds for laboratories abnormalities are shown in Table 10.3.

Table 10.3: Intensity grading scale for laboratories abnormalities

Laboratory Endpoint	Unit	Grade 1	Grade 2	Grade 3
Decrease in WBC	cells / mm3	< LLN to ≥ 3 000	$< 3~000 \text{ to} \ge 2~000$	< 2 000
Decrease in Lymphocytes	cells / mm3	< LLN to ≥ 700	$< 700 \text{ to} \ge 500$	< 500
Decrease in Neutrophils	cells / mm3	< LLN to ≥1 500	$< 1500 \text{ to} \ge 1000$	< 1 000
Decrease in Platelets	cells / mm3	<lln 000<="" 100="" td="" to="" ≥=""><math>< 100~000 \text{ to} \ge 75~000</math>	< 75 000	</lln>	$< 100~000 \text{ to} \ge 75~000$	< 75 000
ALT (increase by factor)		> ULN to < 2.5 x ULN	≥ 2.5 to < 4.0 x ULN	≥ 4.0 x ULN
AST (increase by factor)		> ULN to < 2.5 x ULN	≥ 2.5 to < 4.0 x ULN	≥ 4.0 x ULN

ULN: Upper Limit of Normal LLN: Lower Limit of Normal WBC: white blood cell

ALT: alanine aminotransferase AST: aspartate transaminase

# 10.3.6 Visit to the Center in the Event of Severe (Grade 3) Fever, or Suspicion of Neurotropic Disease or Acute Viscerotropic Disease Within 28 Days of Vaccination

Participants will be instructed to inform (or to visit) the study site if participants develop severe (Grade 3) fever ( $\geq 39.0$ °C, 102 °F).

In the event of specific clinical symptoms (severe [Grade 3] fever, or suspicion of neurotropic diseases or acute viscerotropic diseases) within 28 days of vaccination, specimen (blood, body fluid or tissue samples) might be collected to support the diagnosis according to the local practice. The Investigator or authorized designee will:

- Perform a physical examination (including body temperature) and collect information in the source document
- Collect blood by venipuncture for assessment of biological safetya and detection of YF viremia
- Collect cerebrospinal fluid (CSF) for cultures and virological/bacterial research, when required
- Collect suspected diagnosis
- Treatment will be given according to local practices and standards by local HCPs
   Information collected at this visit will be recorded in the eCRF

\_

<sup>a Biological Safety assessed at local laboratory

In case a neurotropic disease or acute viscerotropic disease is suspected, it is strongly recommended that the Investigator follows the guidelines for the assessment of viscerotropic and neurotropic AEs. On the basis of the severity of the symptoms reported, the Investigator will decide whether body fluid or tissue samples may need to be collected to support the differential diagnosis or vaccine causality. YEL-AVD and YEL-AND will be reported as SAEs. Events suggestive of YEL-AND and YEL-AVD will be assessed as per ACIP case definition criteria.

# 10.4 Appendix: Collection of Pregnancy Information

#### 10.4.1 Definitions

#### Woman of Childbearing Potential (WOCBP)

A woman is considered fertile following menarche and until becoming postmenopausal unless permanently sterile (see below).

If fertility is unclear (eg, amenorrhea in adolescents or athletes) and a menstrual cycle cannot be confirmed before first dose of study intervention, additional evaluation should be considered.

#### Women in the following categories are not considered WOCBP

- 1) Premenarchal
- 2) Premenopausal female with 1 of the following:
  - Documented hysterectomy
  - Documented bilateral salpingectomy
  - Documented bilateral oophorectomy

For individuals with permanent infertility due to an alternate medical cause other than the above, (eg, mullerian agenesis, androgen insensitivity), Investigator discretion should be applied to determining study entry.

Note: Documentation can come from the site personnel's: review of the participant's medical records, medical examination, or medical history interview.

#### 3) Postmenopausal female

A postmenopausal state is defined as no menses for 12 months without an alternative medical cause.

• A high follicle stimulating hormone (FSH) level in the postmenopausal range may be used to confirm a postmenopausal state in women not using hormonal contraception or hormonal replacement therapy (HRT). However, in the absence of 12 months of amenorrhea, confirmation with more than one FSH measurement is required.

Females on HRT and whose menopausal status is in doubt will be required to use one of the non-estrogen hormonal highly effective contraception methods if they wish to continue their HRT during the study. Otherwise, they must discontinue HRT to allow confirmation of postmenopausal status before study enrollment.

#### **COLLECTION OF PREGNANCY INFORMATION**

#### Female Participants who become pregnant

The Investigator will only collect pregnancy information on any female participant who becomes pregnant while participating in this study with an estimated conception date within the 28 days before or after study vaccination. The initial information together with the contraceptive method if any will be recorded on the appropriate form and submitted to the Sponsor within 1 month of learning of a participant's pregnancy.

The participant will be followed to determine the outcome of the pregnancy. The Investigator will collect follow-up information on the participant and the neonate, and the information will be forwarded to the Sponsor. Generally, follow-up will not be required for longer than 4 weeks beyond the estimated delivery date but will be in accordance with local regulations. Any termination of pregnancy will be reported, regardless of fetal status (presence or absence of anomalies) or indication for the procedure.

While pregnancy itself is not considered to be an AE or SAE, any pregnancy complication or elective termination of a pregnancy for medical reasons will be reported as an AE or SAE.

A spontaneous abortion (occurring at < 22 weeks gestational age) or still birth (occurring at > 22 weeks gestational age) is always considered to be an SAE and will be reported as such.

Any post-study pregnancy related SAE considered reasonably related to the study intervention by the Investigator will be reported to the Sponsor as described in Section 8.3.4. While the Investigator is not obligated to actively seek this information in former study participants, he or she may learn of an SAE through spontaneous reporting.

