**Table 1.1: Schedule of activities** 

Phase II Study, 9 or 10 Visits, 1 Vaccination, 8 or 9\* Blood Samples, 5-year Duration Per Participant

Visit/Contact	Collection of information in the CRF	Visit 1	Visit 2†	Visit 3‡	Visit 4	Visit 5	Visit 6	Visit 7	Visit 8	Visit 9	Visit 10
Study timelines (days/months/ years)	N/A	D01	D11	D15	D29	6 M post visit 1	1 Y post visit 1	2 Y post visit 1	3 Y post visit 1	4 Y post visit 1	5 Y post visit 1
_											
	•										
	_	 									

Visit/Contact	Collection of information in the CRF	Visit 1	Visit 2†	Visit 3‡	Visit 4	Visit 5	Visit 6	Visit 7	Visit 8	Visit 9	Visit 10
Study timelines (days/months/ years)	N/A	D01	D11	D15	D29	6 M post visit 1	1 Y post visit 1	2 Y post visit 1	3 Y post visit 1	4 Y post visit 1	5 Y post visit 1
Time windows (days)	N/A	N/A	+2 days	+2 day	+3 days	±15 days	±15 days	±15 days	±30 days	±30 days	±30 days
	I										

Visit/Contact	Collection of information in the CRF	Visit 1	Visit 2†	Visit 3‡	Visit 4	Visit 5	Visit 6	Visit 7	Visit 8	Visit 9	Visit 10
Study timelines (days/months/ years)	N/A	D01	D11	D15	D29	6 M post visit 1	1 Y post visit 1	2 Y post visit 1	3 Y post visit 1	4 Y post visit 1	5 Y post visit 1
Time windows (days)	N/A	N/A	+2 days	+2 day	+3 days	±15 days	±15 days	±15 days	±30 days	±30 days	±30 days
_											

AE: adverse event; AESI: adverse events of special interest, BL: blood sampling; CRF: case report form; D: day; DC: diary card; M: month; MA: memory aid; Min: minutes; mL: milliliter; N/A: not applicable; Pre-vac: pre-vaccination; SAE: serious adverse event; Vac: vaccination

- † Visit 2 to be performed only for the subset of participants submitted to an additional immunogenicity test at D11
- ‡ Visit 3 can be replaced by a phone call only in case the visit cannot be performed at Investigational site (in this case, the physical examination will not be performed)
- § In case of participant discontinuation at a visit, the entire visit will be completed
- \*\*For the entire study period, collection of vaccination with commercial YF vaccine and use of any investigational or non-registered product (drug, vaccine or medical device). Up to Visit 4, collection of concomitant medication.
- ‡‡Only for pregnancies with estimated conception date within the 28 days before or after study vaccination
- †† HIV/Hepatitis B/Hepatitis C serology testing at baseline (Visit 1) will be optional depending on local regulatory requirements.

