#### 5.1 **Inclusion Criteria**

Participants are eligible for the study only if all the following criteria are met:

I01: Aged 18 years up to 60 years on the day of inclusiona

I02: A female participant is eligible to participate if she is not pregnant or breastfeeding and one of the following conditions applies:

> Is of non-childbearing potential. To be considered of non-childbearing potential, a female must be postmenopausal for at least 1 year, or surgically sterile

OR

Is of childbearing potential and agrees to use an effective contraceptive methodb or abstinenced from at least 4 weeks prior to study intervention administration until at least 4 weeksc after study intervention administration.

<sup>a "18 to 60 years" means from the day of the 18th birthday up to the day before the 60th birthday

<sup>b Not applicable for Finland, see Appendix 10.4

<sup>c Except for French participants which have to apply at least 12 weeks contraception after study intervention administration

A female participant of childbearing potential must have a negative highly sensitive pregnancy test (urine or serum as required by local regulation) before any dose of study intervention on Day 1 and the test will be repeated on D29 to confirm the participant is still not pregnant within 28 days of vaccine administration.

Informed consent form has been signed and dateda

I04: Able to attend all scheduled visits and to comply with all study procedures

I05: For participants enrolled in Asian countries as part of the additional cohort only: known Chinese origin, defined as having at least one biological parent of Chinese origin, and will be self-reported by the participant

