#### SAEs

Information on SAEs will be collected and assessed throughout the study, from inclusion at D01 until 6 months after vaccination, and related SAEs and fatal SAEs throughout the study, up to 5 years after vaccination. However, before the study intervention administration, only SAEs related to study procedures are to be collected.

Medical occurrences that begin before the start of study intervention but after obtaining informed consent will not be recorded on the AE section of the case report book (CRF).

All SAEs will be recorded and reported to the Sponsor or designee immediately and under no circumstance should this exceed 24 hours, as indicated in Appendix 10.3. The Investigator will submit any updated SAE data to the Sponsor within 24 hours of it being available.

Investigators are not obligated to actively seek AE or SAE after conclusion of the study participation. However, if the Investigator learns of any SAE, including a death, at any time after a participant has been discharged from the study, and he/she considers the event to be reasonably related to the study intervention or study participation, the Investigator must promptly notify the Sponsor.

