#### 8.3.5 Pregnancy

Pregnancy is an exclusion criterion for enrollment in this study, but a participant could potentially become pregnant during her participation.

Details of all pregnancies in female participants which started within the minimal period of requested contraception (from 4 weeks before to 4 weeksa after study intervention administration) will be collected by the Investigator and recorded in the Pregnancy CRF. The participant will be

\_

<sup>a 12 weeks for France

followed to determine the outcome of the pregnancy. The Investigator will collect follow-up information on the participant and the neonate, and the information will be forwarded to the Sponsor. Any data collected after CRF lock will be transmitted to the pharmacovigilance department on the paper form.

- If a pregnancy is reported, the Investigator should inform the Sponsor within 1 month of learning of the pregnancy and should follow the procedures outlined in Appendix 10.4.
- Abnormal pregnancy outcomes (eg, spontaneous abortion, fetal death, stillbirth, congenital anomalies, ectopic pregnancy) are considered SAEs

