#### 10.5.3 Contraception

• French participants have 12 weeks of contraception after study intervention administration

Sanofi Pasteur
VYF03
517 - vYF
Protocol Version 4.0

• For Finland participants, periodic abstinence is not considered as an adequate method of contraception

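### For French participants, Section 8.3.5 collects pregnancies starting up to 12 weeks after vaccination, but Appendix 10.4 and the schedule footnote stop at 28 days with no French exception

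*Protocol*

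**What the plan says.** Protocol 8.3.5 calls for "Details of all pregnancies in female participants which started within the minimal period of requested contraception", given as 4 weeks before to 4 weeks after study intervention. The footnote on the later limit reads "12 weeks for France". The participant is then followed to the pregnancy outcome, with information on the neonate. Once a pregnancy is reported, the investigator "should follow the procedures outlined in Appendix 10.4".

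The French period matches the contraception requirement elsewhere. The footnote to criterion I02 in 5.1 reads "Except for French participants which have to apply at least 12 weeks contraception after study intervention administration", and 10.5.3 states "French participants have 12 weeks of contraception after study intervention administration".

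Appendix 10.4 says the investigator will collect pregnancy information *only* for a participant who becomes pregnant "with an estimated conception date within the 28 days before or after study vaccination". The Table 1.1 footnote reads "Only for pregnancies with estimated conception date within the 28 days before or after study vaccination", and SAP Table 3.2 repeats it. None of the three mentions France, and 10.5.3 deals with contraception alone.

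**The concern.** The French exception appears in the contraception rules and in 8.3.5, but not in the appendix that gives the pregnancy procedures or in the schedule. The protocol does not say which text prevails. Section 8 treats adherence to the schedule as required, so a French site could apply the 28-day limit in good faith.

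The risk is that a pregnancy conceived on days 29 to 84 after a live-attenuated vaccine is neither recorded nor followed to outcome. SAP 4.2.2.7 lists pregnancies without derivation or imputation, so an unrecorded case cannot be recovered at analysis. The last scheduled pregnancy test named in 8.2.4 is at D29, which is 28 days after vaccination. Learning of a conception in the disputed span therefore depends on participant report, and keeping it depends on the recording rule.

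**Working it through.** **The rules side by side (days counted after vaccination)**

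| Source | France | Other countries |
|---|---|---|
| Protocol 8.3.5 with footnote | 12 weeks = 84 days | 4 weeks = 28 days |
| Protocol Appendix 10.4 | 28 days | 28 days |
| Protocol Table 1.1 footnote | 28 days | 28 days |
| SAP Table 3.2 footnote | 28 days | 28 days |

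Outside France the rules agree. For France they differ by 84 − 28 = **56 days** (days 29 to 84). The wording also differs slightly (pregnancy start in 8.3.5, estimated conception date in 10.4), but that cannot account for eight weeks. All of this is current version 4.0 text.

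**How far SAE collection closes the gap.** Section 8.3.5 classes abnormal pregnancy outcomes as SAEs. Section 8.3.1 collects all SAEs "until 6 months after vaccination, and related SAEs and fatal SAEs throughout the study, up to 5 years after vaccination". Month 6 is day 180 in Table 8.1.

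Gestational age at day 180 = (180 − conception day + 14)/7:
- conception on day 29: (180 − 29 + 14)/7 = 165/7 = 23.6 weeks
- conception on day 84: (180 − 84 + 14)/7 = 110/7 = 15.7 weeks

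Term, assuming 266 days from conception:
- 29 + 266 = day 295
- 84 + 266 = day 350

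Early losses up to about 16 to 24 weeks therefore fall within all-SAE collection. Every term birth falls after it ends. Normal outcomes are not SAEs at any time. A later non-fatal outcome judged unrelated, such as a congenital anomaly found at birth, is outside the SAE rule.

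**Expected number of cases.** The documents do not give French enrolment. Assumptions: France contributes 25% to 50% of the 570 EU participants, half are women, all can conceive, and 1% to 10% conceive per year.

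Expected cases = 570 × French share × 0.5 × annual rate × 56/365.25, where 56/365.25 = 0.1533:
- low: 570 × 0.25 × 0.5 × 0.01 × 0.1533 = 0.11
- high: 570 × 0.50 × 0.5 × 0.10 × 0.1533 = 2.2

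**The case against.** The strongest reply is that the intended rule can be read from the protocol. Section 8.3.5 is the only text that addresses pregnancy collection in France, it ties collection to the contraception period, and it refers to Appendix 10.4 for procedures once a pregnancy is reported, not for the window. A specific country footnote would normally override general text. That is the sensible reading, and the fix adopts it. But no precedence rule is stated, and the restrictive wording in 10.4 and the schedule leaves room for error.

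The Operating Guidelines and the pregnancy CRF are not available here and may already carry the French window. If so, the practical harm shrinks, but the contradiction in the protocol remains.

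It can also be said that the other countries deliberately stop at 4 weeks, so days 29 to 84 are a French requirement and not a window on which the study's safety assessment relies. That is fair, and it limits the stakes. The event range also leans high: a population aged 18 to 60 includes women who cannot conceive, and a 10% annual rate is hard to square with contraception required throughout the disputed span. No case at all is a plausible result.

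Finally, the D29 test does not cause the conflict, and the fix adds no test. It explains only why the recording rule matters.

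**Conclusion.** The concern holds. For French conceptions on days 29 to 84 after vaccination (56 days), 8.3.5 requires collection and follow-up, while Appendix 10.4 and the schedule footnote exclude it. This is an incomplete carry-over of a country exception, and it should be corrected.

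The likely number of affected pregnancies is small, between 0.1 and 2.2 on assumed French share, sex ratio, fertility and conception rate, and probably toward the lower end. The length of the conflict does not depend on those assumptions. The timing of term births rests only on 266 days from conception. No endpoint, estimate or primary analysis is affected; the consequence is confined to the completeness of pregnancy follow-up in one country.

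**What to change.** Apply the 8.3.5 window throughout:

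1. Add an exception of up to 12 weeks after vaccination for France to Appendix 10.4, the Table 1.1 footnote and the SAP Table 3.2 footnote. The SAP change is for consistency only, since it does not instruct sites.
2. Align the pregnancy CRF instruction, and tell French sites in writing that 8.3.5 governs.
3. SAP 5.7 describes randomization in the past tense, so many participants may already be past day 84. Query French sites retrospectively for conceptions on days 29 to 84, at the latest at the next yearly visit.
4. If that query cannot be completed, state the limitation beside the pregnancy listing.

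The cost is wording in three places, one memo, one retrospective query and probably 0 to 2 extra pregnancy follow-ups. No visits or samples are added, because participants are already followed for 5 years (Protocol 4.4).
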